6.6. Dose Modification

Intolerable AEs that lead to treatment discontinuation (except alopecia) will meet criteria to be included in the TFFS endpoint. Intolerable AEs are defined as any study drug-related AE that meets protocol guidance for treatment discontinuation.

- Permanently discontinue treatment for any of:
 - Cabozantinib: development of visceral perforation or fistula formation, severe hemorrhage, serious arterial thromboembolic event (e.g., myocardial infarction, cerebral infarction), nephrotic syndrome, malignant hypertension, hypertensive crisis, persistent uncontrolled hypertension despite optimal medical management, osteonecrosis of the jaw, reversible posterior leukoencephalopathy syndrome
 - Vandetanib: development of prolonged QT interval not improved with electrolyte correction and/or dose reduction, severe skin reactions, ILD, ischemic cerebrovascular events, hemorrhage, heart failure, persistent uncontrolled hypertension despite optimal medical management, or reversible posterior leukoencephalopathy syndrome
 - Selpercatinib: malignant hypertension, hypertensive crisis, persistent uncontrolled hypertension despite optimal medical management, or severe/life-threatening hemorrhage. Patients with clinical benefit who experience recurrent hypersensitivity reaction or recurrent AST or ALT increase despite dose reductions should be

discussed with the Lilly medical team and may be allowed to continue treatment with more than 2 dose reductions if continuation is considered to be safe and in their best interest

Dose reductions should be made according to the following parameters using the dose reduction table below. Interrupt dosing for CTCAE v5.0 Grade 3 or greater AEs or Grade 2 AEs not resolved within 48 hours with appropriate supportive care (e.g., nausea not improved with antiemetics) and considered intolerable by the patient or the investigator.

- For selpercatinib related hypersensitivity, liver function test abnormalities, thrombocytopenia, and hypertension, see dose adjustments below in Sections 6.6.1, 6.6.2, 6.6.3, and 6.6.4, respectively.
- Regardless of treatment arm, study treatment may continue for hypertension that is considered Grade 3 on the basis of requiring ≥ 2 anti-hypertensives or more intensive anti-hypertensive therapy than baseline once blood pressure is stabilized.
- Dose modifications for ECG changes are described in Section 8.2.1. If a patient receiving selpercatinib or cabozantinib experiences QTcF > 500 msec despite 2 dose reductions and if the investigator deems it in the best interest of the patient, the patient may continue treatment with study drug with Lilly medical approval. In addition, Lilly will request a copy of the ECGs for adjudication.
- Upon resolution (or return to patient's baseline) of AEs at least possibly related to treatment, reduce the dose as follows:
 - If previously receiving dose level 1, resume treatment at dose level -1
 - If previous receiving dose level -1, resume treatment at dose level -2
 - If previously receiving dose level -2, resume treatment at the same dose level. If a second AE requiring dose modification occurs at dose level -2, discontinue study treatment.
 - For AEs clearly unrelated to study treatment that resolve or return to patient's baseline in ≤ 14 days, dose reduction is not required.
 - Re-escalation to a prior dose level after a dose reduction is permitted once the AE requiring dose reduction is resolved. See Sections 6.6.1 through 6.6.4 and the IB for specific dose adjustments required for patients receiving selpercatinib.
 - Above are guidelines and may be superseded by local practice guidelines or advice per the local cabozantinib/vandetanib labels when appropriate.

Except as noted, a maximum of 2 dose level reductions will be allowed. Any patient requiring > 42 days omission of treatment for drug-related toxicities will meet the criteria for study treatment discontinuation. Treatment omissions of > 42 days in extenuating circumstances that are not drug-related (e.g. recovery from motor vehicle accident) may be approved by the Lilly medical team.

General Dose Reductions for Treatment Related Toxicities^a

| Dose Level | Time | Selpercatinib Dose (mg) | Cabozantinib Dose (mg) ^b | Vandetanib Dose (mg) |
|---------------|------|-------------------------|-------------------------------------|----------------------|
| Dose Level 1 | AM | 160 | 140 | 300 |
| | PM | 160 | - | - |
| Dose Level -1 | AM | 120 | 100 | 200 |
| | PM | 120 | - | - |
| Dose Level -2 | AM | 80 | 60 | 100 |
| | PM | 80 | - | - |

^a Unless other specific dose reductions, as per Sections 6.6.1, 6.6.2, 6.6.3, and 6.6.4.

In the instance that vandetanib 100-mg tablets are unavailable, but vandetanib 300-mg tablets are available, the below table is to be followed in adult patients.

Vandetanib Dose Modification using 300-mg Tablets for Adult Patients

| Dose Level of Vandetanib | Vandetanib 300-mg tablets ^a |
|----------------------------|--|
| Dose Level 1 | 1 tablet QD every day |
| Dose Level -1 ^b | 1 tablet QD for 2 days, every 3 days |
| Dose Level -2 ^b | 1 tablet QD for 1 day, every 3 days |

Abbreviations: QD = once daily.

^a A starting dose of vandetanib should be 200 mg in adult patients with moderate renal impairment (creatinine clearance results between 30 and 50 mL/min).

^b These dose regimens are expected to give similar reduced exposure corresponding to dose levels -1 and -2 in the standard dose modification table (General Dose Reductions for Treatment Related Toxicities).

Selpercatinib General Dose Reductions for Treatment Related Toxicities for Adolescent Patients

The dose (regardless of BSA calculation) should be no higher than the corresponding adult level for dose adjustments (e.g. Dose Level -1, 120 mg and Dose Level -2, 80 mg). Please see the table in Section 6.1.2 for selpercatinib dose rounding.

| Dose Level | Time | Selpercatinib Dose (mg/m ²) |
|---------------|------|---|
| Dose Level 1 | AM | 92 |
| | PM | 92 |
| Dose Level -1 | AM | 70 |
| | PM | 70 |
| Dose Level -2 | AM | 46 |
| | PM | 46 |

Vandetanib General Dose Reductions for Treatment Related Toxicities and Starting Dose for Moderate Renal Impairment for Adolescent Participants

| BSA (m ²) | Dose Reduction (mg) ^a or Starting Dose with Moderate Renal Impairment |
|-----------------------|--|
| 0.7 - <0.9 | - |
| 0.9 - <1.2 | 100 QOD |
| 1.2 - <1.6 | 100 QD |
| ≥1.6 | 7 day schedule: 100-200-100-200-100-200-100 |

Abbreviations: BSA = body surface area; QD = once daily; QOD = once every other day.

- a Participants with an adverse reaction requiring a dose reduction should stop taking vandetanib for at least a week. Dosing can be resumed at a reduced dose thereafter upon resolution or return to patient's baseline.

See Section 8.2.1 for additional information on dose reduction related to prolonged QTc.

Cabozantinib General Dose Reductions for Treatment Related Toxicities for Adolescent Participants

| BSA (m ²) | Weekly Dose/Schedule for 1 st Dose Reduction due to Toxicity | Weekly Dose/Schedule for 2 nd Dose Reduction due to Toxicity |
|-----------------------|---|---|
| 0.35 – 0.39 | 60 mg = 20 mg M, W, F | Off therapy |
| 0.40 – 0.45 | 80 mg = 20 mg M, W, F, Sun | 60 mg = 20 mg M, W, F |
| 0.46 – 0.55 | 100 mg = 20 mg M, W, Th, Sat, Sun | 60 mg = 20 mg M, W, F |

| BSA (m ²) | Weekly Dose/Schedule for 1 st Dose Reduction due to Toxicity | Weekly Dose/Schedule for 2 nd Dose Reduction due to Toxicity |
|-----------------------|---|---|
| 0.56 – 0.64 | 120 mg = 20 mg M, T, W, F, Sat, Sun | 80 mg = 20 mg M, W, F, Sun |
| 0.65 – 0.78 | 140 mg = 20 mg QD | 100 mg = 20 mg M, W, Th, Sat, Sun |
| 0.79 – 0.90 | 160 mg = 40 mg M, W, F, Sun | 120 mg = 20 mg M, T, W, F, Sat, Sun |
| 0.91 – 1.09 | 200 mg = 40 mg M, W, Th, Sat, Sun | 140 mg = 20 mg QD |
| 1.10 – 1.17 | 200 mg = 40 mg M, W, Th, Sat, Sun | 140 mg = 20 mg QD |
| 1.18 – 1.36 | 240 mg = 40 mg M, T, W, F, Sat, Sun | 160 mg = 40 mg M, W, F, Sun |
| 1.37 – 1.65 | 300 mg = 60 mg M, W, Th, Sat, Sun | 200 mg = 40 mg M, W, Th, Sat, Sun |
| 1.66 – 1.85 | 360 mg = 60 mg M, T, W, F, Sat, Sun | 240 mg = 40 mg M, T, W, F, Sat, Sun |
| 1.86 – 2.07 | 420 mg = 60 mg Daily | 300 mg = 60 mg M, W, Th, Sat, Sun |
| ≥ 2.08 | 420 mg = 60 mg Daily | 300 mg = 60 mg M, W, Th, Sat, Sun |

Abbreviations: BSA = body surface area; QD = once daily.

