6.1.2. Adolescent Dosing

| | Arm A | Arm B1 | Arm B2 |
|---|---|---|---|
| Intervention | Selpercatinib | Cabozantinib | Vandetanib |
| Adolescent Dose ^a | 92 mg/m ² BID (not to exceed 160 mg BID) | 40 mg/m ² | See dosing guide |
| Approximate adult equivalent dose | 160 mg BID | 72 mg QD | |
| Authorized as defined by EU Clinical Trial Regulation | Authorized and used according to EU authorization | Authorized and not used according to EU authorization | Authorized and used according to EU authorization |

Abbreviations: BID = twice daily; QD = once daily.

^a Please refer to nomograms below for the exact dosing.

Adolescent patients will have BSA-adjusted dosing as outlined in the tables below. BSA should be determined according to the Mosteller Formula (Mosteller 1987).

Selpercatinib

Selpercatinib dosing will be rounded according to guidelines in the table below. The maximum starting dose will be no higher than 160 mg BID.

Selpercatinib Capsule Dose Rounding (all doses BID)

| BSA (m ²) | Rounded Dose (mg) |
|-----------------------|-------------------|
| <0.76 | 40 mg |
| 0.76 – <1.2 | 80 mg |
| 1.2 – <1.6 | 120 mg |
| ≥1.6 | 160 mg |

Abbreviations: BSA = body surface area.

Vandetanib**Vandetanib Dosing Nomogram for Adolescent Participants**

| BSA (m ²) | Start dose (mg) ^a |
|-----------------------|------------------------------|
| 0.7 - <0.9 | 100 QOD |
| 0.9 - <1.2 | 100 QD |

| BSA (m ²) | Start dose (mg) ^a |
|-----------------------|--|
| 1.2 - <1.6 | 7 day schedule: 100-200-100-200-100-200-100 |
| ≥1.6 | 200 QD |

Abbreviations: BSA = body surface area; QD = once daily; QOD = once every other day.

^a A reduced starting dose of vandetanib should be used in adolescent patients with moderate renal impairment as per the dose reduction table in Section 6.6.

Cabozantinib

Cabozantinib Dosing Nomogram for Adolescent Participants

| BSA (m ²) | Weekly Dose/ Schedule for Initial Dosing |
|-----------------------|--|
| 0.35 – 0.39 | 100 mg = 20 mg M, W, Th, Sat, Sun |
| 0.40 – 0.45 | 120 mg = 20 mg M, T, W, F, Sat, Sun |
| 0.46 – 0.55 | 140 mg = 20 mg QD |
| 0.56 – 0.64 | 160 mg = 40 mg M, W, F, Sun |
| 0.65 – 0.78 | 200 mg = 40 mg M, W, Th, Sat, Sun |
| 0.79 – 0.90 | 240 mg = 40 mg M, T, W, F, Sat, Sun |
| 0.91 – 1.09 | 280 mg = 40 mg QD |
| 1.10 – 1.17 | 300 mg = 60 mg M, W, Th, Sat, Sun |
| 1.18 – 1.36 | 360 mg = 60 mg M, T, W, F, Sat, Sun |
| 1.37 – 1.65 | 420 mg = 60 mg QD |
| 1.66 – 1.85 | 480 mg = 80 mg M, T, W, F, Sat, Sun |

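### Adolescent selpercatinib reductions are rounded by a BSA-only table that matches the starting dose, so read literally a toxicity reduction can leave the dose unchanged below 1.6 m²

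*Protocol*

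**What the plan says.** Protocol Section 6.6, in the adolescent selpercatinib part, gives three levels in mg/m², each taken morning and evening: "Dose Level 1 | AM | 92", "Dose Level -1 | AM | 70" and "Dose Level -2 | AM | 46". The sentence above the table limits the reduced doses, which "should be no higher than the corresponding adult level for dose adjustments (e.g. Dose Level -1, 120 mg and Dose Level -2, 80 mg"), and the next sentence deals with rounding: "Please see the table in Section 6.1.2 for selpercatinib dose rounding".

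The table it refers to is the capsule rounding table in Section 6.1.2, introduced by "Selpercatinib dosing will be rounded according to guidelines in the table below" and "The maximum starting dose will be no higher than 160 mg BID". It has one BSA column and one dose column, with no column for dose level. Its bands are below 0.76 m² (40 mg), 0.76 to <1.2 (80 mg), 1.2 to <1.6 (120 mg) and 1.6 or more (160 mg).

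For the two comparators, Section 6.6 gives separate BSA-banded tables of reduced adolescent doses. There is no such table for selpercatinib.

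**The concern.** A rounding table whose only input is BSA cannot distinguish 92 from 70 or 46 mg/m². A site that follows the cross-reference looks up the same BSA after a reduction as before and finds the same dose, unless the adult cap happens to be lower.

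Two things are at stake. The first is patient safety in minors. Section 6.6 moves a patient down one level after a related adverse event, and Section 8.2.1 requires a reduction of at least one level on Arm A for qualifying QTcF prolongation. Either step could be carried out on paper with no change in what the patient takes. The second is reporting. The dose-reduction summaries in Protocol Section 9.4.2.5 and SAP Section 8.6.1 could count reductions that did not lower the dose.

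**Working it through.** **Inputs.** Levels 92, 70 and 46 mg/m² and caps 120 and 80 mg (Section 6.6); starting maximum 160 mg and the rounding bands (Section 6.1.2); adult levels 160, 120 and 80 mg BID (general reduction table, Section 6.6).

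**Step 1: the mg/m² levels.** Adult ratios are 120/160 = 0.75 and 80/160 = 0.50. Applied to 92 mg/m² they give 0.75 × 92 = 69 (stated 70) and 0.50 × 92 = 46 (stated 46). The levels agree with the adult scheme, so the difficulty is in the rounding.

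**Step 2: calculated dose at the band limits (level × BSA).**

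| BSA (m²) | 92 mg/m² | 70 mg/m² | 46 mg/m² |
|---|---|---|---|
| 0.76 | 69.9 | 53.2 | 35.0 |
| 1.2 | 110.4 | 84.0 | 55.2 |
| 1.6 | 147.2 | 112.0 | 73.6 |

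The band "0.76 – <1.2 | 80 mg" therefore spans calculated doses of 69.9 to 110.4 mg at the starting level, but 53.2 to 84.0 mg at Level -1 and 35.0 to 55.2 mg at Level -2.

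**Step 3: literal reading.** Dose = the smaller of the Section 6.1.2 value at the patient's BSA and the cap for the level.

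| BSA (m²) | Start | Level -1 | Level -2 |
|---|---|---|---|
| <0.76 | 40 | 40 | 40 |
| 0.76 to <1.2 | 80 | 80 | 80 |
| 1.2 to <1.6 | 120 | 120 | 80 |
| ≥1.6 | 160 | 120 | 80 |

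Only the caps lower the dose: at Level -1 for BSA of 1.6 m² or more, and at Level -2 for 1.2 m² or more. At 1.0 m² the calculated doses are 92, 70 and 46 mg, and the table gives 80 mg each time. At Level -2 that is 80/46, about 1.7 times the calculated dose.

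**Step 4: calculate first, then round.** Three rules were tried, all with the caps. The 40 mg step and 40 mg minimum are assumptions taken from the table values. Below 0.76 m² the dose stays at 40 mg under all three. Elsewhere, Level -1 equals the starting dose in these ranges:

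- nearest 40 mg: about 0.86 to <1.2 m² and 1.43 to <1.6 m²;
- rounding down to 40 mg: about 1.15 to <1.2 m²;
- the table's limits converted to mg at 92 mg/m² (69.9, 110.4, 147.2 mg): about 1.0 to <1.2 m² and 1.58 to <1.6 m².

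Under all three, Level -2 is below the starting dose for every BSA of 0.76 m² or more.

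**Step 5: can the intended rule be recovered from the table?** Nearest-40-mg rounding at 92 mg/m² would put the limits at 60/92 = 0.65, 100/92 = 1.09 and 140/92 = 1.52 m². The table uses 0.76, 1.2 and 1.6. Its rule is not plain nearest-step rounding, so a rule for the reduced levels cannot be inferred from it with confidence.

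**The case against.** The strongest reply is that the literal reading is not the intended one. Section 6.6 prints a lower mg/m² figure for each reduced level, and its cap sentence says that the limit applies whatever the BSA calculation yields. That implies multiplying mg/m² by BSA first and using Section 6.1.2 only to reach a capsule strength. On the literal reading the mg/m² rows would serve no purpose. This has force: a reader might infer that the protocol directs sites to keep the dose unchanged, and the text does not support that. But the calculate-first reading still lacks a rounding rule, and plausible rules give different doses to the same patient.

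Part of the unchanged dose also reflects capsule steps. Near 1.14 m², 70 mg/m² is itself about 80 mg, so an unchanged 80 mg at Level -1 agrees with the calculation there. That stands, but it does not explain 80 mg at Level -2 in the same band.

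Some toxicities follow their own rules (Sections 6.6.1 to 6.6.5), and the protocol points to the Pharmacy Manual, labels and Investigator's Brochure for dose modification. Those sources may hold the missing rule, so the point is limited to what the protocol itself says. Sections 6.6.1 and 6.6.2 do not fill the gap, because they refer to an adolescent equivalent dose without defining it.

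Finally, few patients are likely to be affected. Section 2.2 calls adolescent MTC rare, enrolment under 18 depends on local permission, Germany excludes minors, and the Netherlands requires an age of at least 16.

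**Conclusion.** The point holds as a defective cross-reference. Read literally, the first reduction leaves the dose unchanged below 1.6 m² and the second leaves it at the starting level below 1.2 m². From 1.2 to <1.6 m² only the first fails, and at 1.6 m² or more the caps make both work. Read as calculate-first, the reduced dose is undetermined because no rounding rule is stated.

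A reader might infer that TFFS would count reductions that never happened. It would not. In Protocol Section 9.4.3.2.1 and SAP Table JZJB.7 the events are BICR progression, qualifying toxicity leading to discontinuation, and death. Only one TFFS sensitivity analysis (SA1, SAP Table JZJB.8) uses reductions, and it counts a third reduction on Arm A for three named toxicities. In the main analysis any effect is indirect: a patient who passes through two nominal reductions and then discontinues under the Section 6.6 rule could become an event without the dose having fallen.

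Sample size, power and type I error are not affected. The documents give neither the expected number of adolescents nor their BSA distribution, so the number in the affected bands cannot be stated. The sensitivity ranges rest on the assumed 40 mg step and minimum; the literal table needs no such assumption. The clarification is worth making because it concerns a safety instruction for minors.

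**What to change.** Reconcile the mg/m² levels, the adult-level caps and the Section 6.1.2 rounding table so that each reduced selpercatinib level has one explicit dose per BSA band, in the form already used for adolescent vandetanib and cabozantinib. State whether the dose is calculated before rounding, and define the adolescent equivalent dose used in Sections 6.6.1 and 6.6.2. If the Pharmacy Manual already holds the rule, bring it into the protocol or refer to it there. Which doses are right is for the sponsor's clinical team, and none is proposed here.

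For reporting, check adolescent dose-reduction records against the dose actually dispensed before they are tabulated. The cost is a table clarification in the protocol and a note to sites. The statistical analyses need no change.

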6.6.1. Dose Modifications for Selpercatinib Hypersensitivity

If selpercatinib drug hypersensitivity is suspected, study drug should be held and treatment with steroids at 1 mg/kg prednisone (or equivalent) should be initiated. Upon resolution, selpercatinib may be resumed at a reduced dose of 40 mg BID (or adolescent equivalent dose) while continuing steroids at the same dose. Note that this dose reduction does not require sponsor approval. Hypersensitivity has recurred in some patients, typically at 3 to 6 hours following drug administration.

Discontinue selpercatinib for recurrent clinically significant hypersensitivity. In the absence of clinically significant recurrent drug hypersensitivity, the dose of selpercatinib may be escalated sequentially to 80 mg BID, 120 mg BID, and 160 mg BID (or adolescent equivalent doses) for a minimum of 7 days at each dose. Once the patient has tolerated treatment for a minimum of 7 days at the final dose, steroids may be tapered slowly.

6.6.2. Dose Modifications for Selpercatinib Related Liver Test Abnormalities

If a patient experiences Grade ≥ 3 elevated hepatic lab increases (ALT, AST, or direct bilirubin), study drug should be held and evaluation for potential alternative causes should be conducted (e.g., history of other hepatotoxic medications/substances, viral serologies, liver imaging). The grading is according to Common Terminology Criteria for Adverse Events (CTCAE) version 5.0 with slight modification as described in Section 8.3. A repeat value 3 to 5 days after the initial finding of elevation of labs should be obtained to confirm the abnormality and to confirm if it is increasing or decreasing. Thereafter, hepatic labs should be monitored at least weekly until resolution to normal/baseline (depending on the clinical situation, resolution to Grade 1 if baseline is normal may be acceptable but awaiting normalization is preferable. If the abnormalities do not begin to resolve (or worsen) within 5 days of the AE, a hepatology consultation should be considered to evaluate the need for a liver biopsy. Due to the question of a

possible immune component to the lab abnormalities observed, some patients with persistent increases have initiated treatment with steroids, with subsequent improvement.

Upon resolution, selpercatinib may be resumed at a reduced dose of 2 dose levels lower than at which the abnormalities occurred with weekly lab monitoring. In the absence of recurrent abnormalities, the dose of selpercatinib may be escalated sequentially to the next higher dose level after a minimum of 2 weeks at the lowest dose level, and again to the dose level at which the abnormalities occurred after a minimum of 4 weeks at the dose level below which the abnormalities occurred. Once the patient has been treated at a stable dose of selpercatinib for a minimum of 4 weeks without recurrent lab abnormalities, the frequency of monitoring may be decreased (e.g., every 2 weeks for 2 months and then monthly thereafter). For patients who experience Grade ≥ 3 elevated hepatic labs on a dose of 80 mg BID (or adolescent equivalent dose), the Lilly medical team should be contacted for additional guidance to determine if continuation with dose modification is acceptable. If the patient experiences \geq Grade 3 elevated ALT, AST, or direct bilirubin at a dose of 40 mg BID, selpercatinib should be discontinued.

Please refer to Section 8.2.2. for additional monitoring that may need to be initiated.

6.6.3. Dose Modifications for Thrombocytopenia

If a patient is discovered to have thrombocytopenia Grade ≥ 3 , study drug should be held and the patient should be evaluated for alternative causes (medications/substances, viral studies). A hematology consultation may be considered, as necessary, to understand the etiology and to consider a role for concomitant steroid therapy. The patient should undergo weekly CBC testing until the event has recovered to normal/baseline. Upon recovery to Grade 1 or better, the patient should resume selpercatinib at a reduced dose of one dose level reduction (if thrombocytopenia is determined to be related to selpercatinib) with weekly CBC surveillance for 1 full cycle.

6.6.4. Dose Modifications for Hypertension

For the purpose of the study, hypertension is defined as

- a sustained increase in blood pressure from baseline, as evidenced by ≥ 2 readings on ≥ 2 separate occasions, or
- a clinically significant elevation requiring acute treatment.

If hypertension occurs, study drug may be interrupted at the discretion of the investigator while

- a new anti-hypertensive medication regimen is initiated, or
- a pre-existing regimen is optimized to a reproducible reading of $\leq 140/90$ mmHg.

If study drug is interrupted, it may be resumed at the same or a lower dose at the discretion of the investigator. In all cases, the patient should continue to undergo regular blood pressure monitoring to ensure adequate blood pressure control.

